## BACKGROUND/RATIONALE

Chronic inflammatory demyelinating polyneuropathy (CIDP) is an autoimmune neurological disorder that causes limb weakness and numbness. Many patients require immunosuppressants and plasma exchange (PLEX) to control their symptoms. Intravenous immunoglobulin (IVIG) is also an effective treatment (Hughes et al, 2006 & 2008; Hughes, 2009; Cocito et al, 2010), and the American Academy of Neurology (AAN) guideline recommended that it should be offered in the long-term treatment of CIDP (Patwa et al, 2012). While effective, IVIG causes systemic side effects in about 5% of patients. These side effects include rash, pruritus, myalgia, fever, chills, headache, low back pain, nausea, vomiting, changes in blood pressure or heart rate, renal failure, and aseptic meningitis (Berger, 2008). For many patients who are chronically treated with IVIG, venous access may be a problem over time. An alternative is the subcutaneous (SC) route, which has been in use since 1980 for primary immune deficiency disorders and is the treatment of choice for this condition in Scandinavia and England (Radinsky et al, 2003). As compared to IV route, SC route maintains higher trough levels of immunoglobulins, increases patient independence, reduces systemic side-effects, and is better tolerated in those who are pregnant or sensitized to IgA (Radinsky et al, 2003). In a review of side effects associated with 33,168 SCIG infusions, no severe or anaphylactoid reactions occurred (Gardulf et al, 1995). Patients can self-administer medication, and hence, overall cost may be reduced. A retrospective study of 28 children with primary immunodeficiency in Canada showed that the mean difference in costs between IVIG and SCIG during the study period (1 year on IVIG and 1 year on SCIG) was \$4,346 in favor of SCIG (Ducruet et al, 2011). Gardulf et al (1995) also reported a reduction of US\$10,100 in cost per year per patient with SCIG use in Sweden. Similar cost savings were achieved in other countries as well (Lazzaro et al, 2014; Zbrozek, et al, 2014). Disadvantages of SCIG include more frequent infusions and local reactions at sites of infusion (transient swelling, soreness, redness, induration, local heat, and itching) in about 1% of patients.


## SPECIFIC AIMS

As of October 2012, we identified more than 70 patients with the diagnosis of CIDP at the University of South Florida (USF) Neurology Clinic. We estimated that at least 2/3 of these patients meet the Inflammatory Neuropathy Cause and Treatment (INCAT) Group diagnostic criteria (Sander & Latov, 2003). Many of these patients still attend our clinic and many are dependent on IVIG to control symptoms. Data are lacking in terms of tolerability, although our physicians are often contacted by patients or infusion centers for guidance regarding treatment of Ig infusion related side effects such as hypertension, flu-like symptoms, headaches, and joint pain.

Specific Aim #1. This study will assess the QOL and adverse events experienced by patients on IVIG and whether patients currently treated with IVIG would be willing to try the SC route of administration. This specific aim will be achieved via telephone or face-to-face survey. The goal is to identify factors that may reduce the patients' willingness to consider alternate drug delivery method.

Specific Aim #2. For patients willing to switch to SCIG, this study will test the hypothesis that SCIG is safe and well tolerated and can be self-administered by patients with CIDP. We will monitor patients' adverse reactions via patient diary, questionnaires, examination, and laboratory studies.

Specific Aim #3. To test the hypothesis that SCIG is associated with better QOL, we will compare QOL measures pre- and post-treatment.

Specific Aim #4. We will collect clinical data to test the hypothesis that SCIG is efficacious in controlling the symptoms of CIDP. Patients will be followed with hand-held dynamometry (HHD) and 20-ft timed walk. Pre- and post-treatment scores will be compared using appropriate statistical analysis.

## RESEARCH STRATEGY

### **SIGNIFICANCE:**

We have a substantial number of CIDP patients who require frequent doses of IVIG. Due to the side effects and time required by the IV route, these patients would potentially benefit from SCIG for the reasons discussed. The purpose of this pilot study is to determine whether SCIG is well tolerated, can be self-administered, improves QOL, and is efficacious in controlling CIDP symptoms.

### **INNOVATION:**

Currently, most if not all CIDP patients who required Ig treatment are receiving it via the IV route. If proven efficacious and better tolerated, SCIG would be an attractive alternative. Additional benefits of SCIG include lesser cost and increased convenience to patients.

### **APPROACH:**

This is a prospective, open label study of SCIG for the treatment of patients with CIDP who are dependent on IVIG for control of symptoms.

**Participants:** Up to 30 patients with IVIG-dependent CIDP will be enrolled. To qualify, a patient must meet **ALL** of the inclusion criteria and **NONE** of the exclusion criteria.

**Inclusion Criteria:**

- 1) Confirmed diagnosis of CIDP (having 2 or more of the following):
  - a) Weakness in any limb
  - b) Motor fatigue significant enough to interfere with ADL's or work
  - c) Paresthesia of sufficient severity to require medication
  - d) Sensory impairment
  - e) Walking impairment
- 2) Requires IVIG to control symptoms
- 3) Male or female patient, older than 18 years of age
- 4) Able to provide informed consent
- 5) Able to be trained to provide self-injection
- 6) Willing to be on birth control for the duration of the study (for women of reproductive potential)

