Specific Aim #4. To test the hypothesis that SCIG is efficacious in controlling the symptoms of CIDP.

Clinical response to SCIG will be monitored using HHD and 20-ft timed walk. Data from pretreatment and SCIG treatment phase will be compared. The HHD will measure force generated by the following muscle groups: Shoulder flexion, elbow flexion, elbow extension, wrist extension, first dorsal interosseous (hand), hip flexion, knee extension, knee flexion, ankle dorsiflexion. Measurement will be done bilaterally in duplicates. For the primary efficacy endpoint, HHD muscle strength measured at Week 24 will be compared to HHD muscle strength measured at baseline (pretreatment)

Secondary End-Point.

1. Progression of symptoms requiring reversion to IVIG, initiation of PLEX or other medications, or hospitalization.

**Study Timeline and Feasibility:** Participants will be recruited from the USF Neuromuscular Clinic. This Clinic is the tertiary referral center for the west coast of Florida, with a population of more than 4 million in the Tampa Bay region alone. We estimated that we have more than 70 patients with CIDP. In addition, we see an average of 2 new CIDP patients per month. Thus, there are enough patients for a 3 to 1 screening to enrollment ratio. Planned recruitment is an average of 1 patient every 1.5 months, for a total of 22.5 months. This schedule will place the final recruit completing the trial during month 30 and afford time during the final 6 months of the study for analyzing and preparing data for publication. This planned recruitment timeline is feasible given the size, established referral patterns, and historical recruitment experience of this clinic.

**Rescue protocol:** If a subject worsens (or “relapses”) during the study, we will institute a rescue protocol. Relapse is defined as a 20% decrease in force (as detected on HHD) in more than 50% of the muscles tested when compared to baseline. In case of relapse, we will quantify the serum Ig levels, give IVIG 1 g/kg boost followed by SCIG at 2 g/kg per month. If the subject is already on 2 g/kg per month of SCIG, we will switch the patients back to IV administration and/or institute other treatment options (steroids, PLEX). Please see algorithm in Appendix 2. We will also switch back to IVIG if, at any point during the study:

- a. The subject requests the switch due to treatment failure, adverse events or patient preference.

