- b. The investigators consider it to be in the best interest of the subject (i.e., due to intolerable side-effects, pregnancy, or noncompliance).

**Potential Pitfalls and Alternative Strategies:** There is the potential that some patients may lose interest or become too reticent in performing self-administration. Since compliance may be an issue with self-administration of an injectable medication, serum IgG levels will be done to monitor patient’s adherence to protocol. The use of a home journal for recording therapy and a weekly telephone call will encourage compliance. In the scenario where there is concern with patient compliance, a weekly home therapy visit will be done. Attrition is also expected during the course of the study. If a participant becomes a ‘drop out,’ his or her data will be used in the analysis using an intention to treat protocol. Finally, while recruitment can be an issue in clinical trials, our planned enrollment rate of an average of 1 patient per 1.5 months is feasible. Furthermore, we already identified several patients who are appropriate for this trial. With an average of 2 new CIDP patients seen per month in the USF Neuromuscular Clinic, we should be able to recruit the remaining patients in the proposed timeline. Furthermore, there are many more CIDP patients in the greater Tampa region who are not being seen at USF. Thus, there is an untapped pool of subjects available. In the unanticipated scenario that we fall behind on subject recruitment, we have incorporated 6 additional months in our timeline for analysis and manuscript preparation that could be utilized for subject recruitment and treatment.

**Data Management and Quality Control:** Physiologic and questionnaire data will be collected across two time points (pre- and SCIG treatment phase) by the PI and coordinator who are all proficient in these testing methods. To ensure participant confidentiality, data will be coded to remove patient identifiers into a password-protected database (Excel) on a central computer system that is backed up daily. Data accuracy will be verified by double data entry. All original paper questionnaires will be locked in the PI’s office with only coded identifying information. There will be an interim analysis done after 8 patients have completed the study.

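### The progression endpoint counts starting a new therapy but not increasing an existing one, and does not say whether the protocol's own relapse rescue is an event

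*Combined protocol and SAP*

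**What the plan says.** The Approach section describes the design: "This is a prospective, open label study of SCIG for the treatment of patients with CIDP who are dependent on IVIG". There is no control arm, and the enrolment target is a ceiling: "Up to 30 patients with IVIG-dependent CIDP will be enrolled".

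The inclusion criteria give the diagnosis as "Confirmed diagnosis of CIDP (having 2 or more of the following", followed by five clinical features, and add "Requires IVIG to control symptoms". Only two exclusion criteria concern CIDP treatment: an upper limit on the current monthly IVIG dose, and recent participation in a trial of an investigational product for CIDP. Neither touches steroids, immunosuppressants or PLEX in ordinary use. The Background says of CIDP in general: "Many patients require immunosuppressants and plasma exchange (PLEX) to control their symptoms".

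Under Specific Aim #4, the primary efficacy endpoint compares HHD strength at Week 24 with baseline. The Secondary End-Point is "Progression of symptoms requiring reversion to IVIG, initiation of PLEX or other medications, or hospitalization".

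Three other places bear on this:

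- The treatment description under Specific Aim #2 says SCIG dosing is individualised, partly by patient response.
- The Rescue protocol defines relapse as a 20% fall in HHD force in more than half of the muscles tested. It prescribes an IVIG boost of 1 g/kg followed by SCIG at 2 g/kg per month. For a patient already at that SCIG dose it prescribes a switch back to the IV route and/or other treatments.
- Safety Monitoring says concomitant medications are reviewed at every study visit. No analysis rule uses that information.

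**The concern.** Aim 4 asks whether SCIG controls CIDP symptoms. With no control arm, the progression endpoint is the main place where failure of SCIG would show. If a patient worsens and the response is more of something already being taken, the endpoint as worded records nothing.

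The same patient then has HHD measured at Week 24. If the increase worked, the value is near baseline and is read as strength maintained on SCIG, although it was maintained on SCIG plus more treatment. Both results err in the same direction, towards apparent control.

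**Working it through.** The plan has no figure to reproduce: it states no expected progression rate, no margin and no power calculation. The check is to take each way in which worsening could be treated and ask whether the endpoint wording captures it.

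| Response to worsening | Where permitted | Event as worded? |
|---|---|---|
| Lasting return to IVIG | Rescue protocol | Yes (reversion) |
| New drug, or PLEX for the first time | Rescue protocol | Yes (initiation) |
| Hospital admission | Not restricted | Yes |
| Higher dose of a steroid or immunosuppressant already taken, or more PLEX in a patient already receiving it | Nothing in the entry criteria or monitoring text prevents it | No |
| Higher SCIG dose because of response | Treatment description, Aim #2 | No |
| Relapse treated by IVIG boost, then SCIG at 2 g/kg per month | Rescue protocol, first branch | Unclear |
| Relapse in a patient already at 2 g/kg per month of SCIG | Rescue protocol, second branch | Yes, by switch to IV or by initiation |

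**The rescue row.** The boost is IVIG, so one could call it reversion. But the patient continues on SCIG, and the protocol describes switching back to IV as a separate, later step. One could call the boost initiation of another medication, but the patient was on IVIG at entry. The text does not settle it.

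**Consequence across patients.** The planned weekly SCIG dose is 0.25 to 0.5 g/kg. Over four weeks that is 4 × 0.25 = 1 g/kg to 4 × 0.5 = 2 g/kg per month, as the protocol states. Within that range, only a patient at the top goes straight to the second branch. Two patients with the same protocol-defined relapse can therefore be classified differently because of the SCIG dose they happened to be on.

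**Effect on Week 24 HHD.** Table 2 schedules HHD monthly from Week 4. A patient who meets the relapse definition at, say, Week 8, is rescued and recovers by Week 24 contributes a paired difference near zero to the signed-rank test. No rule marks that value. The intention-to-treat sentence under Potential Pitfalls deals with drop-outs, not with patients who stay in after an increase.

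**Size per patient.** Each patient whose worsening is treated this way and not counted lowers the progression proportion by 1/n.

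- At the ceiling of 30 patients: 1/30 = 3.3 percentage points.
- At the accrual rate and period stated under Study Timeline and Feasibility: 22.5 months ÷ 1.5 months per patient = 15 patients, so 1/15 = 6.7 percentage points.

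The number of such patients cannot be derived. The documents report neither how many clinic patients take background therapy nor how often it is raised.

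**The case against.** **In the plan's favour.** This is a self-described pilot. The listed Primary End-Points are withdrawal for side effects and discontinuation for laboratory abnormalities, and neither depends on this wording. Reversion to IVIG and hospitalization, arguably the clearest failures, are already events. Concomitant medications are reviewed at each visit, so much could be recovered afterwards. The Appendix 2 rescue algorithm is a figure not reproduced in the text available here; if it classifies rescue as progression, that part of the point falls away. All of this limits the weight of the point. It does not supply a rule for increases, and deciding after the data are seen which increases count would be post hoc.

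It is also fair to say that Week 24 HHD regardless of later treatment answers a legitimate question about the whole management strategy. That is why the all-patient result should stay. It does not by itself answer whether SCIG controlled the disease.

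**Stronger readings the documents do not support.**

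- A reader might infer that two non-specific features are enough for entry. Every inclusion criterion must be met, and "Requires IVIG to control symptoms" is one of them. What can be said is that dependence is required in words but no evidence standard is given.
- A reader might take "We estimated that at least 2/3 of these patients meet the Inflammatory Neuropathy Cause and Treatment (INCAT) Group diagnostic criteria" to mean that a third of enrolled patients will not need immunoglobulin. Two thirds is a floor. It describes all clinic CIDP patients as of October 2012, before the IVIG requirement is applied, and failing research criteria does not show that a patient would stay well untreated.
- A reader might infer from "With an average of 2 new CIDP patients seen per month in the USF Neuromuscular Clinic" that some participants will still be improving on recent IVIG. New to a referral clinic does not mean newly treated.
- A reader might conclude that stable strength cannot be credited to SCIG because of the entry criteria. That limit comes mainly from the single-arm design without a margin, and it would remain under any entry criteria.

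**Conclusion.** The point holds for the endpoint and for the reading of Week 24 HHD. As written, worsening managed by increasing an existing CIDP therapy is not a progression event, the status of the protocol's own rescue is undetermined, and HHD after either is analysed as response to SCIG.

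The effect on the reported progression proportion is 3.3 percentage points per affected patient at 30 patients and 6.7 at 15. The total is unknown. The direction for progression is certain if any such patient occurs. For HHD it rests on the assumption that the increase improves strength.

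The conclusion assumes that initiation carries its ordinary meaning of starting something not already in use, and that no classification of rescue appears in the Appendix 2 figure. The point does not establish that enrolled patients lack CIDP or do not depend on IVIG.

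**What to change.** 1. **Endpoint.** Keep the existing triggers and the condition that they arise from progression of symptoms. Extend the initiation trigger to initiation or dose increase, and name immunoglobulin alongside PLEX and other medications. State that a protocol-defined relapse leading to rescue is an event. This reconciles the Secondary End-Point with the Rescue protocol and leaves every treatment rule as it is. Splitting the same weekly dose over more days is not a dose increase.
2. **Baseline.** Record background CIDP therapy (drug, dose, PLEX schedule) with the Medical History already taken at Screening.
3. **Analysis.** Beside the all-patient Week 24 HHD comparison, prespecify a second one in which patients with such an increase or rescue count as not maintained on SCIG, identified from the concomitant medication review already planned at each visit. Rewording the endpoint alone would leave the HHD comparison untouched, so this step is needed. In the signed-rank test, these patients can be given the worst rank.
4. **Description only.** INCAT status and the chart evidence for IVIG dependence may be recorded to describe the cohort. A subset analysis is not asked for: its size is unknown and it would be small.

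The cost is a few words in the endpoint, one baseline record and one added analysis. The reported progression rate may rise.

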**Exclusion Criteria:**

- 1) Thrombocytopenia or other bleeding disorders;
- 2) Patients on anticoagulation therapy with an INR > 3.5;
- 3) Severe or anaphylactoid reactions to IVIG;
- 4) Cancer (active or currently treated);
- 5) Pregnancy;
- 6) Breast-feeding;
- 7) Renal insufficiency (creatinine > 1.5 upper limit of normal) or failure;
- 8) Congestive heart failure;
- 9) Psychiatric illness that would interfere with ability to provide informed consent or adhere to protocol;
- 10) Current IVIG doses greater than 2 g/kg per month;
- 11) Subject with an IgA level < 5% lower limit of normal;
- 12) History of active infection with HIV, Hepatitis B or Hepatitis C;
- 13) Presence of any other medical condition, which in the opinion of the investigator might interfere with performance;
- 14) Participation in a trial of an investigational medicinal product for CIDP in the past 12 weeks.

**Sample size and statistical analysis:** Descriptive information for the rate of change, such as mean and standard deviation, will be calculated. Due to the small sample size and self-control used in this study, instead of using paired t-test, Wilcoxon paired ranked test will be used to compare the change of before and after from each patient. Significance level is defined as 0.05 and all of the analyses will be carried by SAS (version 9.2).

**DESIGN:** The study will be submitted to the USF IRB for approval.

**Specific Aim #1.** We will assess QOL using the Medical Outcome Study 36-item short form health status scale (SF-36) and the Rasch-built Overall Disability Scale (R-ODS). The scales have been validated in patients with CIDP (Merkies et al, 2002; van Nes et al, 2011). We will also do a survey of side effects and satisfaction with treatment (using the Treatment Satisfaction Questionnaire for Medication, or TSQM) and CIP-PRO20 scale (used by permission from [name]; see appendix 3). No surveys will be completed until the patient signs the ICF. In addition, we will determine whether patients currently treated with IVIG would be willing to try the SC route of administration. Reasons cited for unwillingness to switch will be collected.

Specific Aim #2. To test the safety and tolerability of SCIG and feasibility of self-administration in patients with CIDP.

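### Entry sets no minimum time on IVIG and no stable dose or interval, so a trend already under way at baseline can be counted as a SCIG effect

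*Combined protocol and SAP*

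**What the plan says.** The combined protocol and SAP has two IVIG entry rules, both under Approach. Inclusion Criteria item 2 reads "Requires IVIG to control symptoms". Exclusion Criteria item 10 removes patients with "Current IVIG doses greater than 2 g/kg per month". No section asks for a minimum time or number of courses on IVIG, an unchanged dose or interval, a run-in, or agreeing strength readings before the switch. The only look-back of fixed length in the criteria concerns something else, in exclusion item 14: "Participation in a trial of an investigational medicinal product for CIDP in the past 12 weeks".

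The Participants paragraph states "Up to 30 patients with IVIG-dependent CIDP will be enrolled", and Specific Aim #2 under Design describes 1 to 2 g/kg per month as the clinic's usual maintenance range. Neither dependence nor maintenance is defined. The Participants paragraph makes qualification turn on the listed criteria.

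On design, the Approach says "This is a prospective, open label study of SCIG", and no control arm is described. Specific Aim #4 makes the primary efficacy endpoint HHD strength at Week 24 against pretreatment HHD. The statistical paragraph tests each patient's change with a Wilcoxon paired test at 0.05. Specific Aim #3 compares pretreatment quality of life and treatment satisfaction with the SCIG phase. No analysis adjusts for time on IVIG or for a trend before the switch.

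On recruitment, Study Timeline and Feasibility cites more than 70 clinic patients plus 2 new ones per month and concludes "Thus, there are enough patients for a 3 to 1 screening to enrollment ratio". Potential Pitfalls and Alternative Strategies says several suitable patients are already known, adds "With an average of 2 new CIDP patients seen per month in the USF Neuromuscular Clinic, we should be able to recruit the remaining patients", and then points to further patients in the region who are not seen at the clinic.

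**The concern.** A single-arm switch study reads every change since baseline as the result of the switch. That is safe only if patients are on a plateau when baseline is measured. A patient can have genuine CIDP, genuinely need IVIG, and still be gaining strength because IVIG was started or increased recently. A patient whose IVIG was increased after a bad spell adds regression to the mean in the same direction. A patient who is slipping, or whose baseline is taken soon after a course, can push the change the other way.

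The HHD, timed-walk, R-ODS and SF-36 comparisons are all exposed. A rising trend could produce an apparent benefit, or hide a loss caused by the switch. With no control arm, and no record of time on IVIG required, the analyst cannot repair this afterwards.

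**Working it through.** **1. What the criteria let through.** Take a patient some weeks into IVIG at 1 g/kg per month, judged to need it and meeting every other criterion. Inclusion item 2 is met and exclusion item 10 does not apply. No rule looks at the start date or the last dose change. A patient with many stable years on IVIG passes in the same way. The protocol's own Table 1 shows that both extremes occur in practice: among reported patients moved to SCIG, time on IVIG runs from one course to 16 years.

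**2. Whether the schedule would reveal a trend.** Under Specific Aim #2, SCIG starts within 2 weeks of the last IVIG course. Table 2 places HHD and medical history at both Screening and Day 1. The documents set no interval between those visits and no rule on agreement between the two readings.

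**3. Recruitment arithmetic.**
- Planned accrual: 22.5 months ÷ 1.5 months per patient = 15 patients. The ceiling is 30, which at that rate would take 30 × 1.5 = 45 months. Both sizes are used below.
- New patients over the accrual period: 2 × 22.5 = 45.
- Patients available: 70 + 45 = 115. New share: 45 ÷ 115 = 39%. This is an upper bound on the new share of these two sources, because the existing pool is given as more than 70. It counts patients new to the clinic, who are not necessarily new to IVIG.

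**4. Illustration of size.** The documents give no SD of HHD change, effect size or power, so there is no figure of the plan to reproduce. Assume that the switch has no effect, that changes are normal with SD 1, and that a fixed number of patients carries an upward trend of d SDs. Each scenario is 10,000 simulated trials with the exact two-sided Wilcoxon signed-rank test at 0.05 (the plan does not state sidedness). The share with a trend is set at 20% and at 39%; rounded to whole patients, 39% becomes 40%. Mean bias = share × d.

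| n | Patients with trend | d | Mean bias (SD) | Significant improvement |
|---|---|---|---|---|
| 15 | 0 | – | 0 | 2.2–2.3% |
| 15 | 3 (20%) | 0.5 | 0.10 | 4.9% |
| 15 | 3 (20%) | 1.0 | 0.20 | 8.0% |
| 15 | 6 (40%) | 0.5 | 0.20 | 9.7% |
| 15 | 6 (40%) | 1.0 | 0.40 | 21.6% |
| 30 | 0 | – | 0 | 2.2–2.6% |
| 30 | 6 (20%) | 0.5 | 0.10 | 7.4% |
| 30 | 6 (20%) | 1.0 | 0.20 | 13.6% |
| 30 | 12 (40%) | 0.5 | 0.20 | 16.8% |
| 30 | 12 (40%) | 1.0 | 0.40 | 44.7% |

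The model is symmetric, so a downward trend of the same size gives the same rates of false worsening. The error grows with n, because a larger trial detects the trend more reliably.

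**The case against.** A reader might infer that the trial will be filled with newly treated patients. Two new patients per month at 3 to 1 screening is 2 ÷ 3 = 0.67 per month, exactly the planned 1 per 1.5 months. The documents do not support that inference. The ratio is stated after both the existing pool and the new patients have been named, several candidates are already identified, and unseen regional patients are a further source. At a tertiary referral clinic, new means new to the clinic; some will be long-treated referrals. Nor do the documents show that any enrolled patient's strength will be rising, so it cannot be said that a false SCIG effect will occur, or by how much.

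The references to dependence and to a usual maintenance dose do suggest established patients. That probably describes the intent and lowers the likely share of recent starters. But neither term is defined or made a condition of entry, and a patient can depend on IVIG while still improving on it.

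It can also be said that strength gained over the 24 weeks is gained while on SCIG, so crediting SCIG is not simply false. This stands in part for Specific Aim #4, which concerns symptom control. It does not help Specific Aim #3, which claims better quality of life than on IVIG. Even under Aim #4, a rising trend can mask a loss.

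Two further points stand. This is a pilot, and the endpoints headed primary concern withdrawal for side effects or laboratory abnormalities, which this bias does not directly touch. The two scheduled pre-switch HHD readings also allow a crude look at trend, although the plan makes no such use of them.

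**Conclusion.** The gap is real: the criteria do not secure the stable baseline that the before-after comparisons need, and patients still changing on IVIG can be enrolled. Any such change can be counted as a SCIG effect, most likely as improvement but possibly as worsening. Newly seen patients are one possible source, not the only one.

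The actual size is unknown. The illustrated rates, from 4.9% to 44.7% against about 2.5%, rest wholly on the assumed share and trend. They show that a moderate trend in a minority of patients would be enough to mislead; they do not estimate the bias in this trial. The point bears on the HHD, walk and quality-of-life conclusions. It is a worthwhile, inexpensive improvement rather than a fatal defect.

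**What to change.** Add two conditions to inclusion item 2: a minimum time on IVIG, and a period of unchanged IVIG dose and interval before Screening. Both are needed, because a patient who has just started on a constant dose meets a stability rule and may still be improving. Twelve weeks is one example, matching the look-back in exclusion item 14, but that item has no stated link to a plateau on IVIG, so the investigators should set and justify the length. Allow a patient who fails either condition to be re-screened once stable.

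Record IVIG start date, dose, interval and date of last change under the medical history already taken at Screening. Report Week 24 HHD and quality-of-life changes by time on IVIG, descriptively only, since the groups will be small.

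The cost is one eligibility line, four history fields and one extra table. Recently started or adjusted patients enter later: at 12 weeks, 84 days or about 2.8 months. The pool of more than 70 patients and the 6-month reserve can absorb that, although the reserve is also the time set aside for analysis and writing. The results will then describe patients established on IVIG, which is the population the Participants paragraph already names.
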